### **Statistical Analysis for Specific Aim 2**

Specific Aim 2 is to determine the impact of an aerobic intervention on CVR. Similar to Aim 1, we will test each BOLD change value jointly using a linear mixed-effects model to determine whether the mean change of the groups is significantly different across the time points (Pre and Post). Fixed effect will be group (Spin vs Control) and the random effect will be time (Pre vs Post). Additional analyses will use multiple regressions to describe the effect by participant demographics (gender, race, age, and hypertensive status) or by MoCA score. An FDR of  $q = 0.05$  will be calculated and used to correct for multiple test and effect sizes will be computed.

### **Statistical Analysis for Specific Aim 3**

The task fMRI BOLD images will be processed for slice-timing correction, and each image volume will be corrected for rigid-body head motion. The volume registered images will be inspected for artifacts induced by motion, cardiac pulsation and respiratory cycles and removed spatio-temporally using Independent Component Analysis (ICA). These artifact-free images will then be spatially transformed to MNI space using linear and non-linear co-registration algorithms. Following this spatial transformation, the images will be smoothed within the brain to increase the signal-to-noise ratio. Then the images will be scaled to accurately determine the relative percent signal change in BOLD induced by the task. Finally, task-induced BOLD changes ( $\Delta$ BOLD) from pre- to post-aerobic intervention and corresponding hemodynamic response functions are quantified using deconvolution technique.

Since the goal of this aim is to quantify the impact of baseline physiologic measures (ie, resting blood flow and CVR) on task-induced BOLD changes, we plan to accomplish this task by modeling the contributions of perfusion and CVR to  $\Delta$ BOLD responses. The equations below describe our simple modeling approach using linear regression:

$$\Delta BOLD_{i,ROI} = A + B \cdot CBF_{i,ROI} + C \cdot CVR_{i,ROI} + D \cdot (CBF_{i,ROI} \times CVR_{i,ROI})$$

Where subscript  $i$ =pre or post session, ROI refers to the regions of interest, and coefficients A is the modeled intercept, B and C are modeled slopes for perfusion and CVR contributions, and D is modeled slope for the interaction between perfusion and CVR respectively. We will compare the slopes obtained for pre and post exercise to explore (a) how each of the baseline measures (ie, perfusion and CVR) change in response to exercise, and (b) within each condition (pre or post), disentangle perfusion and vascular influence on task-induced BOLD change. Also, modeling for the interaction will account for the coupling effect which by itself can provide insightful information in terms of exercise-induced perfusion-CVR coupled effects. We plan to carry out the

above processing and modeling at the ROI level as it renders more detection power and is computationally less intensive. From a statistical standpoint, we will compute the F score to test the significance of overall fitting of the model, and we will also obtain the  $t$  score for each predictor (perfusion and CVR) to test the significance of their association with change in measured variable ( $\Delta$ BOLD). To evaluate responsiveness to training and its impact on the model, post hoc analysis will include stepwise multiple regression to evaluate delta VO2 on perfusion and CVR in a-priori ROIs as well as behavioral outcomes.

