### 2. Abstract:

This study will examine cerebrovascular function in older Veterans before and after a proven aerobic exercise intervention, allowing us to better understand the robust impact of exercise on brain function and health. Task-based fMRI and the resultant BOLD map is currently a dominant method of neurocognitive investigation, particularly related to documenting the beneficial changes demonstrated with rehabilitation. No single imaging technique can resolve the complexities of imaging neural plasticity in brain systems, therefore we propose a solution of combining imaging techniques and modeling the impact of perfusion and CVR on the BOLD response. We will model the hypothesized change in perfusion and CVR to the BOLD response following the intervention to quantify the percentage of variance both perfusion and CVR account for in the task-induced BOLD signal. This will allow us to understand the degree to which change in perfusion and CVR impacts the well-documented beneficial change in task-induced BOLD following exercise.

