#### **4. Specific Aims:**

The study will enroll 134 older, sedentary adults. Participants will be pseudorandomized to one of two 12-week intervention conditions: Aerobic Exercise or Stretching.

**Specific Aim 1:** To determine the effect of a 12-week aerobic exercise intervention on changes in cerebral perfusion using arterial spin labeling in older Veterans.

*Hypothesis:* Compared to a non-aerobic intervention Control group, the aerobically trained group will have increased basal perfusion in areas that demonstrate age-related decline and are malleable to aerobic exercise (inferior frontal and motor cortices).

**Specific Aim 2:** To determine the effect of a 12-week aerobic exercise intervention on changes in cerebrovascular reactivity using a hypercapnic CO2 response test in older Veterans.

*Hypothesis:* Following the interventions, aerobically-trained older adults will have increased CVR to CO2 in the inferior frontal and motor cortices when compared to controls.

**Specific Aim 3:** To quantify the impact of cerebrovascular perfusion and cerebrovascular reactivity on the BOLD response during task-based (cognitive executive and motor) fMRI.

*Hypothesis:* Perfusion and CVR will account for a significant portion of variability in the BOLD response during task-based fMRI both before and after the intervention.

*Measures for Specific Aim 3.*

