## **7. Statistical Analysis:**

### **Statistical Analysis for Specific Aim 1**

Specific Aim 1 is to determine whether there will be a statistically significant difference in the cerebral perfusion data between the two groups (Spin and Control) following the intervention. We will assess the perfusion values jointly using a linear mixed-effects model to determine whether the mean change in perfusion between the groups is significantly different. For the model the fixed effect will be group (Spin vs Control) and the random effect will be time (Pre vs Post). We expect that modeling the outcomes jointly will increase the statistical power. This model will enable us to estimate the

overall effects of time and the interventions, and most importantly, how the effects of the interventions differ with time. Additional analyses will use multiple regressions to describe the effect of participant demographics such as gender, race, age, hypertensive status as well as MoCA score. A false discovery rate (FDR) of  $q = 0.05$  will be calculated and used to correct for multiple tests and effect sizes will be computed.

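### Aim 3 tests perfusion and CVR in a product-term model with no stated centring, so the t scores refer to slopes at CVR = 0 and CBF = 0; the pre/post slope change is credited to exercise without a control contrast

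*Combined protocol and SAP*

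**What the plan says.** Section 7, Statistical Analysis for Specific Aim 3, gives the model ΔBOLD = A + B·CBF + C·CVR + D·(CBF × CVR), indexed by session (pre or post) and ROI. It explains that "B and C are modeled slopes for perfusion and CVR contributions, and D is modeled slope for the interaction between perfusion and CVR respectively". The model is to be judged by an overall F, and perfusion and CVR each by a t "score for each predictor (perfusion and CVR) to test the significance of their association with change in measured variable". The only scaling described is of the BOLD images. No centring or reference value is given for CBF or CVR, and the equation has no group term.

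The section gives two uses for the slopes. One is to compare pre with post "to explore (a) how each of the baseline measures (ie, perfusion and CVR) change in response to exercise". The other, within each session, is to "disentangle perfusion and vascular influence on task-induced BOLD change".

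The wider goal is variance explained. The Abstract wants to "quantify the percentage of variance both perfusion and CVR account for in the task-induced BOLD signal", and the hypothesis in Section 4 is that "Perfusion and CVR will account for a significant portion of variability in the BOLD response during task-based fMRI". Power Analysis and Sample Size bases Aim 3 on 88 subjects and an R² increase of 0.111. A Spin-versus-Control comparison is specified for Aims 1 and 2 (for Aim 1, "to determine whether the mean change in perfusion between the groups is significantly different") but not for Aim 3.

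**The concern.** In a model with a product term, each lower-order coefficient is a slope at the zero of the other variable. These are valid conditional slopes, but no participant has zero resting blood flow, so they do not describe association at the physiology the trial will observe. B and C are also the only per-predictor quantities offered for separating perfusion from vascular influence. The joint test could be sound while the individual t scores are non-significant, or carry the opposite sign to the slope at average physiology, only because of where zero lies.

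The second issue is causal wording. With no group term, a slope change that happens in both arms alike would count as a response to exercise. Nor does a change in slope show how perfusion or CVR themselves changed; it shows a change in their relation to ΔBOLD.

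**Working it through.** **The plan's own figure.** With f² = 0.111/0.889 = 0.1249 and λ = 0.1249 × 88 = 10.99, the noncentral F at alpha 0.05 gives power 0.783 for 3 numerator df, 0.839 for 2 and 0.906 for 1. The plan does not state the df. The 3-df reading is within two points of the stated 0.80, which would need R² = 0.115. This figure does not depend on centring.

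**Algebra.** The CBF slope is B + D·CVR and the CVR slope is C + D·CBF. So B is the CBF slope at CVR = 0, and C is the CVR slope at CBF = 0. Centring changes B and C but leaves the fit, F, R² and the t for D the same (simulated differences below 1e-10).

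**Size of the centring effect.** The documents give no mean, SD or correlation for CBF or CVR. Assumptions:
- normal predictors with equal SD/mean k, uncorrelated, scaled to SD 1;
- residual SD 1, N = 88, two-sided alpha 0.05;
- slopes at the mean of √(0.1249/2) = 0.25, which gives R² = 0.111 when D = 0.

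On this scale the mean is 1/k, so B = 0.25 − D/k. The slope at the mean and D are each estimated with SE of about 1/√N, so SE(B) is about √(1 + 1/k²) times the centred SE. The simulation used 6,000 replicates per setting.

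| k = SD/mean | 0.15 | 0.2 | 0.3 | 0.5 | 1.0 |
|---|---|---|---|---|---|
| SE ratio, formula | 6.7 | 5.1 | 3.5 | 2.2 | 1.4 |
| SE ratio, simulated | 7.0 | 5.3 | 3.6 | 2.3 | 1.4 |
| Power for B, D = 0 (centred 0.60–0.62) | 0.07 | 0.08 | 0.10 | 0.17 | 0.36 |
| Power for B, D = −0.2 (centred 0.61–0.63) | 0.54 | 0.57 | 0.64 | 0.72 | 0.79 |
| True B, D = +0.2 | −1.08 | −0.75 | −0.42 | −0.15 | +0.05 |
| Estimated B negative, D = +0.2 (centred 1–2%) | 92% | 91% | 86% | 72% | 37% |

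True B changes sign once D exceeds 0.25k. With correlation 0.3 and the same R² (slope √(0.1249/2.6) = 0.219, D = 0), power is 0.06–0.27 uncentred against 0.46–0.48 centred. With N = 44 (uncorrelated, D = 0) it is 0.06–0.18 against 0.33–0.34.

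The opposite error also occurs. With zero slopes at the means, an interaction of 0.3, correlation 0.3 and SD/mean of 0.15–0.30 for CBF and 0.20–0.50 for CVR, the uncentred t tests reject in 68–76% of runs, against about 6% centred.

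**Which arms enter.** The 88 subjects equal 44 + 44, the per-group size in Power Analysis and Sample Size, which suggests both arms pooled. But the Aim 3 text says ΔBOLD changes "from pre- to post-aerobic intervention and corresponding hemodynamic response functions are quantified using deconvolution technique", which could mean Spin only. Neither reading gives a controlled comparison.

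**Size of the attribution problem.** Assumptions: 44 per arm, centred predictors, D = 0, pre/post correlation 0.6 for predictors and 0.5 for residuals. The variance of a slope change on n people is about (2 − 2 × 0.6 × 0.5)/n = 1.4/n. The SEs are therefore about:
- √(1.4/88) = 0.126 for both arms pooled;
- √(1.4/44) = 0.178 for Spin only;
- √(2.8/44) = 0.252 for the arm contrast.

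Simulated rejection rates when the CBF slope rises equally in both arms, so that there is no exercise effect:

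| Shared rise | Pooled, 88 | Spin only, 44 | Arm contrast |
|---|---|---|---|
| 0 | 5% | 5% | 5% |
| 0.25 | 48% | 25% | 5% |
| 0.40 | 86% | 53% | 5–6% |

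**The case against.** The strongest reply is that Aim 3's goal, hypothesis, overall F and power figure all concern variance explained, and none depends on centring. That stands, and it limits the point to the t scores and slope comparisons.

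Centring may also be intended but unwritten. If main effects were tested before the product entered, their t scores would not depend on centring (power 0.60–0.64). The reference to an increase in R² is compatible with that order. But neither is in the text, and the t tests are described straight after the equation with the product.

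The magnitudes rest on assumed inputs, and even the direction varies: at D = −0.2 uncentred power matches or exceeds centred power from SD/mean 0.3 upward, though for a different slope. SD/mean of 1.0 with normal predictors implies about 16% negative values, so that column is an extreme. An interaction of 0.2 is nearly as large as the assumed slopes of 0.25. This criticism of the size is fair; the algebra needs none of these inputs.

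The pre/post comparison is labelled exploratory, Aims 1 and 2 already compare the arms, and the shared rises of 0.25 and 0.40 have no basis in the documents. The rejection rates also use a z test on the simulated SD, as a stand-in for a real test. They are therefore illustrations. An exploratory label still does not support a causal reading.

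Finally, the arm contrast has low power: 14% for a Spin-only slope change of 0.25 and 29% for 0.40. The pooled test does no better (14% and 31%), because pooling halves the effect (0.25 × 44/88 = 0.125) as well as the SE. A Spin-only test has more power (25% and 53%) but cannot separate exercise from anything else that changes over 12 weeks.

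**Conclusion.** Both parts of the concern hold. As written, the t scores for perfusion and CVR test slopes at CVR = 0 and CBF = 0, and the plan has no basis for attributing a pre/post slope change to exercise. The first follows from the equation, provided no unstated centring or staged entry is intended. The second holds whichever arms are analysed.

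The size is uncertain. Under the stated assumptions with no interaction, power for the perfusion t score falls from about 0.6 to between 0.07 and 0.36. With an interaction the coefficient can gain power or change sign, because it is then a different quantity and not a poor estimate of the same one. The overall F, R², the test of D, the variance-explained hypothesis and the 0.111 figure are sound on this point. The plan should be corrected before analysis, but the main Aim 3 test is not at risk.

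**What to change.** - **Centring.** Within each ROI, centre CBF and CVR at one stated value common to both sessions, for example the pre-session mean of all analysed participants, before forming the product. Interpret B and C as slopes at that value. Keep the overall F, R² and the test of D as planned.
- **Arms.** State which arms enter the Aim 3 model and which group is the control. Section 4 names stretching, Section 5 labels the stretching programme as interval exercise and adds a wait-list control, and Section 6 lists three conditions; these need reconciling.
- **Attribution.** Keep the slope comparison exploratory. Attribute a slope change to exercise only from a Spin-versus-Control contrast of the pre/post slope change, in one model that allows for repeated measures on the same person (a person random effect or person-clustered standard errors). Take changes in perfusion and CVR themselves from Aims 1 and 2.

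Centring is a wording change; if it is already intended, one sentence settles it. With a common value, the slopes refer to that value and not to each session's own mean. The gap is D times the shift in mean: 0.2 × 0.5 SD = 0.10 residual SD, for example. Session-specific centring would show that same 0.10 as a slope change although the relation had not changed.

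The contrast costs precision. Its SE is √(2/44)/√(1/88) = 2.0 times that of a pooled change on 88, and √(2/44)/√(1/44) = 1.41 times that of a Spin-only change on 44.

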### **Power Analysis and Sample Size**

For Aim 1, we used preliminary data comparing older active adults to older sedentary adults. Effect size for difference in inferior frontal perfusion for a small sample ( $n=10$ ) was  $d=2.740$ . If this effect size is taken as an estimate of the effect size for change in the Spin group with  $n=44$  and  $\alpha$  FDR-corrected to 0.0261, then power approaches 1.00. A more conservative estimated change in perfusion being half the effect, with the standard deviation remaining constant, would produce an effect size of 1.370. With the same  $n$  and  $\alpha$  as above, the power still approaches 1.00. The required effect size to achieve a power of 0.80 would be  $d=0.5$ , which would seem quite achievable given our preliminary data. Hence, the power should be more than adequate and seems plausible based on what we know. Because we want to maintain sensitivity at this level, the study is powered mainly to this Aim, while power for Aims 2 and 3 is more than adequate. For

example, for Aim 3, with  $\alpha < .05$ , minimum power of 0.80 and 88 subjects, we have the power to detect an increase in  $R^2$  as small as 0.111 in each ROI. We have detected significant correlations between BOLD response in M1 and IFG with smaller sample sizes (n=36 and n=41, respectively). Accounting for much less than 11% of the variance in criterion variables with the predictors would be too little variance to provide information useful for the design of future clinical trials. Hence, we should have the power to detect effects large enough to impact future clinical trials.

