For behavioral data, we estimate the effect size for semantic fluency from 2 sources of data using the same treatment we will use for this study. For our lab the effect size for change in the Spin group was  $d=1.804$ , and for the preliminary data from an ongoing study the effect size for change in semantic fluency was  $d=1.410$ . Using the more conservative of the two estimates,  $n=44$  and a FDR corrected  $\alpha=0.0261$ , power approaches 1.00. Again, an effect size of  $d=0.5$  would achieve a power of 0.80, which seems quite achievable given the large effect sizes in two independent samples. Use of the Control in this instance is problematic because of a large negative outlier, yielding a large negative mean (-2.000, indicating a loss of semantic fluency) and a large standard deviation. Even so, these data yield an effect size of  $d=0.886$ , but these data are not stable enough to yield a good estimate of between-group effect size. With  $n=44$  per group and  $\alpha=.05$  (FDR corrected), an effect size of  $d=0.64$  would yield a power of 0.80. Based on the strong effect size for Spin, we believe this is an achievable effect size for a between-group analysis based on what we know about the Spin intervention.

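### The post hoc analysis of training response uses stepwise regression, which inflates the coefficients it keeps; fixed models with delta VO₂ always reported would avoid this at small cost

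*Combined protocol and SAP*

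**What the plan says.** Section 7, Statistical Analysis for Specific Aim 3, ends with a follow-up step on how training response relates to the imaging measures: "post hoc analysis will include stepwise multiple regression to evaluate delta VO"₂ on perfusion and CVR "in a-priori ROIs as well as behavioral outcomes". The stated purpose is responsiveness to training and its effect on the Aim 3 model. The text does not say which variable is the outcome, which are the candidates, what the entry and removal rules are, whether the arms are pooled, or how multiple tests are handled.

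The surrounding analyses are specified differently:

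- The Aim 3 hypothesis is tested with a fixed three-term regression (perfusion, CVR and their product), for which "we will compute the F score to test the significance of overall fitting of the model", with a t test per predictor.
- Aim 1 has an FDR of q = 0.05, "used to correct for multiple tests and effect sizes will be computed"; Aim 2 has a similar rule.
- The Specific Aims name the regions in advance, for instance "inferior frontal and motor cortices".
- Behavioral and Self-Report Data lists submaximal VO₂ among the behavioural variables and plans Spearman correlations of behavioural performance with the primary outcomes.

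**The concern.** The variables and regions are already named, so little needs to be searched for. Stepwise regression keeps a term because its estimate in this sample was large enough, then reports that estimate with a p-value and interval computed as if the term had been fixed beforehand. Retained slopes are therefore too large on average, and the reported precision cannot be trusted.

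If delta VO₂ is among the candidates, a second problem follows: the procedure may discard it, leaving no estimate for the question asked. What is at stake is the description of how fitness gain relates to perfusion, CVR and behaviour. An inflated slope could mislead whoever plans the next study.

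**Working it through.** **Inputs from the plan.** Two a-priori regions; 44 per group, 88 if pooled; alpha 0.05 for Aim 3.

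**Assumptions, because the plan is silent.** Entry at p<0.05, removal at p>0.10; 4, 6 or 10 candidates; candidate correlation 0 or 0.5; one true standardized slope of 0.20. Four candidates would arise from perfusion and CVR in two regions if delta VO₂ were the outcome.

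**1. The plan's own figure.** Power Analysis and Sample Size says that with "minimum power of 0.80 and 88 subjects, we have the power to detect an increase in" R² "as small as 0.111 in each ROI". With f² = R²/(1−R²) = 0.111/0.889 = 0.125 and λ = f²·N = 0.125 × 88 ≈ 11.0, the noncentral F test gives:

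| Tested predictors | Power at 0.111 | Minimum detectable R² increase |
|---|---|---|
| 2 | 0.839 | 0.102 |
| 3 | 0.783 | 0.115 |

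The stated 0.111 lies between the two, so it is broadly reproduced. It concerns the fixed model; no figure is given for the stepwise step.

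**2. Why selection inflates.** At the first step, a candidate enters at p<0.05 only if its sample correlation exceeds t/√(t²+n−2):

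- n=88: 1.988/√(3.952+86) = 0.21
- n=44: 2.018/√(4.072+42) = 0.30

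Both thresholds exceed the assumed true value of 0.20, so an estimate that enters at that step must overshoot.

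**3. Simulated size.** True slope 0.20, candidate correlation 0.5, 2,000 runs per setting:

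| n | Candidates | True term kept | True term dropped | Mean slope when kept | Ratio to 0.20 | Mean slope, fixed model |
|---|---|---|---|---|---|---|
| 88 | 4 | 39.2% | 60.8% | 0.297 | 1.49 | 0.198 |
| 88 | 10 | 32.7% | 67.3% | 0.323 | 1.62 | 0.202 |
| 44 | 4 | 22.3% | 77.7% | 0.404 | 2.02 | 0.199 |
| 44 | 10 | 18.1% | 81.9% | 0.430 | 2.15 | 0.196 |

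A separate run gives 0.29–0.31 at n=88 and 0.38–0.40 at n=44. There, coverage of the nominal 95% interval for a selected slope falls to 84–88% at n=44, against about 95% for the fixed model.

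**4. What should not be counted.** With no true effects and n=88, stepwise selection admits at least one predictor in about 14%, 27% and 38% of analyses with 3, 6 and 10 candidates. But 1−0.95^k is 14.3%, 26.5% and 40.1%, and a fixed model with the same independent predictors shows at least one p<0.05 in 13.9%, 26.0% and 39.6%. With four independent candidates the two approaches both give 17.9%. This is ordinary multiplicity. Nor is it fair to set these rates against the 4–5% rejection rate of a single overall F test, which asks a different question.

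**5. Cost of the fixed model.** Power for one term worth R² 0.111 at n=88 is 0.906 with either 1 or 3 predictors in the model; at n=44 it is 0.629 and 0.628. Correlation between predictors costs more. If delta VO₂ correlated 0.5 with group (an assumption), the variance factor would be 1/(1−0.25) = 1.33 and the standard error would grow by √1.33 = 1.15.

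**The case against.** The strongest reply is that little depends on this step. It is labelled post hoc, Aims 1 and 2 use mixed models with FDR control, and the Aim 3 hypothesis rests on a fixed model. That stands and limits the weight of the point. The label does not remove the bias in whatever is reported.

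Second, the wording can be read with delta VO₂ as the outcome, in which case it cannot be dropped. If it were the sole candidate predictor, nothing would be selected at all. The first reading is open, so the risk of losing delta VO₂ is conditional; the inflation of retained slopes applies either way. The second sits poorly with the word stepwise and the several measures listed.

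Third, fixed models do not themselves control false positives. Four tests (perfusion and CVR in two regions) give 1−0.95⁴ = 18.5% if independent, before any behavioural outcome. That is correct, so a multiplicity rule has to be part of the change.

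Fourth, adjusting for group alters the question. The aerobic arm is meant to raise fitness and the comparator is kept below the aerobic training zone, so conditioning on group leaves mainly the association within arms. Omitting group lets the slope partly repeat the arm difference. Neither is the only right choice, which is why both should be shown.

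Finally, the plan also mentions the effect on the BOLD model. The models proposed here do not cover that; if it is wanted, its model needs stating separately.

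**Conclusion.** The point holds as a minor improvement to a post hoc analysis. Under the assumed settings, a true standardized slope of 0.20 is overstated by about half when selected at n=88 and roughly doubled at n=44, the size if one arm is analysed alone. A fixed model on the same data averages 0.20. These sizes depend on the number of candidates, their correlation, the entry rule and the true slope, none of which the plan gives.

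Three stronger conclusions that a reader might draw are not supported:

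- That this is the plan's only look at fitness and outcome. The text says the post hoc work will include it, and the planned Spearman correlations may cover submaximal VO₂.
- That stepwise selection causes the 14–38% false-entry rates. A fixed model with as many predictors gives nearly the same.
- That the main results or the sample size are threatened. No primary aim or sample-size figure depends on this step.

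**What to change.** Replace the stepwise sentence with pre-specified linear models, one per outcome: perfusion and CVR in each a-priori region, and each behavioural outcome, listed by name. Each model takes the post-intervention value as the outcome, with delta VO₂ as the fixed term of interest and the baseline value of that outcome as covariate. Show the delta VO₂ coefficient with and without group, and state that the adjusted version describes the association within arms.

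Report every delta VO₂ coefficient with its 95% CI whatever its p-value; showing only the significant ones would bring the same bias back. Apply the plan's FDR of q = 0.05 across these tests and keep the post hoc label.

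The change takes a few sentences in section 7 and needs no further participants or data. The downside is a few degrees of freedom and slightly wider standard errors, mainly in the version that includes group.
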